**Hackensack University Medical Center
Institutional Review Board**

NCT03896230 Unique Protocol ID: Pro2018-0970

Comparison of ketamine 0.1 mg/kg, 0.2 mg/kg, and 0.3 mg/kg intravenous doses for acute pain in the emergency department: A prospective, randomized, double-blind, active-controlled, clinical trial

**[name], BCPS
Emergency Medicine Clinical Pharmacist
Hackensack University Medical Center**

Study Team:

**[name]
[name], BCCCP
[name]**

Version - 4/20/2021

Table of Contents

I.	Objectives of the Study.....	3
II.	Background Material.....	3-5
III.	Drug Information.....	5-6
IV.	Inclusion Criteria.....	6
V.	Exclusion Criteria.....	6
VI.	Recruitment Procedures.....	6
VII.	Definitions.....	7
VIII.	Methodology.....	7-8
IX.	Statistical Considerations.....	8-10
X.	Discomfort and Risks.....	10
XI.	Benefits.....	10
XII.	Criteria for Evaluating Response.....	10
XIII.	Confidentiality.....	10
XIV.	Credentials, Training.....	11
XV.	Bibliography.....	11-13
XVI.	Appendix A.....	14-15
XVII.	Appendix B.....	16-18

I. Objectives of the Study

Primary Objectives

This study will prospectively compare the mean Numerical Rating Scale (NRS) pain score reduction amongst three recommended dosing strategies of intravenous ketamine (0.1 mg/kg, 0.2 mg/kg, and 0.3mg/kg) for acute pain in the emergency department (ED).

Secondary Objectives

This study will also examine the frequency of adverse events secondary to ketamine including fatigue, dizziness, nausea, headache, feeling of unreality, changes in hearing or vision, mood changes, generalized discomfort, and hallucinations, changes in vital signs. Subgroups for exploratory analysis based on the need for rescue analgesia within two hours of ketamine administration, adequate pain relief, previous opioid tolerance, and age (adults < 65 years old and > 65 years old).

II. Background Material

Pain is one of the most common reasons for presentation to the emergency department, with studies reporting it being responsible for up to 78% of visits. Accordingly, pain reduction is one of the primary goals of emergency medicine.¹ Opioids are among the most common analgesics used to treat pain in the emergency department.² The increasing use of opioids has made treating acute pain difficult due to increased concern for opioid tolerance, abuse, and misuse.³

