- Alcohol or drug abuse
- Received an analgesic within the last four hours
- History of congestive heart failure
- History of aortic or brain aneurysm
- Active Chest Pain
- Porphyria
- Active methadone treatment
- Pregnant or breastfeeding
- Signs of respiratory, hemodynamic, or neurologic compromise
 - Systolic blood pressure < 90 mmHg or > 180 mmHg
 - Heart rate < 50 beats per minute or > 150 beats per minute
 - Respiratory rate < 10 breaths per minute or > 30 breaths per minute
 - Glasgow Coma Score < 15
- Previously received ketamine ≤ 0.3 mg/kg IV for acute pain in the emergency department

VI. Recruitment Procedures

This is a single-center, prospective, randomized, double-blind, active controlled trial that will identify patients in the emergency department with acute pain who meet the eligibility criteria from January 2019 through January 2021 to achieve a sample of at least 180 patients.

VII. Definitions

Adequate pain relief:

- A score decrease on the Numerical Rating Scale (NRS) by ≥ 3 points

Moderate pain:

- A NRS score of 4-7 out of 10 per hospital policy

Severe pain:

- A NRS score of 8-10 out of 10 per hospital policy

Rescue analgesia:

- Any IV analgesic to be determined by the treating provider

Opioid tolerant:²⁵

- Patients receiving, for one week or longer, at least 60 mg oral morphine/day, 25 mcg transdermal fentanyl/hour, 30 mg oral oxycodone/day, 8 mg oral hydromorphone/day, 25 mg oral oxymorphone/day, or an equianalgesic dose of another opioid

VIII. Methodology

This is a single-center, prospective, randomized, double-blind, active-controlled trial. Patients who meet inclusion criteria and none of the exclusion criteria will be enrolled from January 2019 to January 2021 to achieve a goal sample size of 180 patients. Data such as demographics, self-reported pain score, adverse drug events, vital signs, and need for rescue analgesia within two hours of ketamine administration will be reported. Outcomes will include pain score reduction, incidence and severity of adverse drug events, adequate pain relief, and need for rescue analgesia within two hours of ketamine administration. All data will be entered in a password protected data sheet for proper analysis. No patient identifying data will be recorded.

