The administration of ketamine 0.1 – 0.3 mg/kg IV for acute pain in the Adult Emergency Department was approved at the September 2018 Pharmacy and Therapeutics Committee and is currently standard of care. Education was provided to all providers and nurses in the emergency department.

Patient screening, enrollment, and data collection will be performed by the treating resident or attending who will remain blinded. The Primary Investigator will also remain blinded and the ED pharmacists will be unblinded to facilitate ordering and delivery of the study drug.

Patients who consent to the study and meet eligibility criteria will be randomized to one of three doses of ketamine (0.1 mg/kg, 0.2 mg/kg, or 0.3 mg/kg) to be given IV infusion over 20 minutes. The block randomization list will be generated by the Hackensack Meridian Health Biostatistician prior to patient enrollment. Pharmacy investigators will maintain the randomization list and deliver the medication to the nurse in a blinded fashion. The medication will be prepared as a 0.1 mg/kg, 0.2 mg/kg, or 0.3 mg/kg dose in a 100 mL solution of dextrose 5% or sodium chloride 0.9% according to the predetermined randomization list. If there is a significant delay from the initial pain score to the study dose of ketamine administration, the patient will be withdrawn from the study and receive standard of care treatment. If pain is not controlled after the administration of ketamine, providers can order a rescue analgesic of their choice.

Patient history will be reviewed for known allergies, resuscitative equipment will be readily available, and the type and intensity of pain prior to administration will be documented. Baseline

vital signs, such as blood pressure, heart rate, and respiratory rate, will be assessed prior to IV administration of ketamine and at 120 minutes after infusion or upon discharge, whichever is sooner. The patient's self-reported pain score, need for rescue analgesia, and any adverse drug effects will be reassessed within 15 minutes from the end of the infusion and then every 30 minutes for up to 120 minutes or until discharge, whichever is sooner. Incidence, severity, and total number of adverse drug events will be documented using the Side Effects Rating Scale for Dissociative Anesthetics (SERSDA).

Procedure:

- Patient consent, screening, and enrollment will be performed by the treating resident or attending who will remain blinded
- Patient will be assigned a subject number

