- Treating resident or attending will notify the ED pharmacist that a patient has been enrolled in the trial
- ED pharmacist will notify the IV room and place the study drug order
- Either the ED pharmacist or a pharmacy supervisor will randomize the subject based on the predetermined randomization list
- Study drug will be prepared as 0.1 mg/kg, 0.2 mg/kg, or 0.3 mg/kg IV dose in a 100 mL solution of dextrose 5% or sodium chloride 0.9%
- ED pharmacist will promptly deliver the study drug to the ED
- Baseline vital signs will be assessed prior to starting the study drug infusion
- Study drug will be administered via IV infusion over 20 minutes
- Treating resident or attending will reassess the patient at 15 minutes from the end of infusion, at 30 minutes from the end of infusion, and then every 30 minutes for up to 120 minutes or until discharge, whichever is sooner

IX. Statistical Considerations

Randomization

The study participants will be randomly assigned into one of the three dose groups in the ratios of 1:1:1. Block randomization will be used to balance the sample size in each group.

Primary Outcome

The primary outcome is the numerical rating scale (NRS) pain score reduction from baseline to 120 minutes after the injection. The null hypothesis is that there is no difference among those three doses with respect to the mean score reduction.

Describing Data

The continuous variables (such as age of participant at the time of study) will be summarized using mean, median, standard deviation, interquartile range, range, minimum and maximum. The discrete variables (such as sex) will be summarized using frequency and percentage.

Exploring Differences

The two-sample Student's t-test will be used to compare the continuous variables between groups. If the normality assumption is violated, the Wilcoxon rank sum test will be used. The Shapiro-Wilk test will be used to evaluate the normality. The one-way analysis of variance (ANOVA) will be used to compare the continuous variables among groups. The Bartlett test will be used to evaluate the homogeneity of variances. The Tukey Honest Significant Differences test will be used to perform the multiple comparisons. If the normality assumption or homogeneity of variances assumption is violated, the Kruskal-Wallis one-way ANOVA by ranks will be used. The Dunn test will be used to perform the multiple comparisons.

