The chi-square test will be used to compare the categorical variables between or among groups. If the expected frequency in any cell of the contingency table is less than 5, the Fisher's exact test will be used.

The 95% confidence interval on the variables of interest will be calculated. The 2-sided p value will be reported for each test. A p value of 0.05 or less will be considered an indication of statistical significance.

Exploring Associations

When necessary, graphical techniques will be used to display the statistical results. The scatter plots will be used to explore the associations between two continuous variables, and the Pearson's correlation coefficient or Spearman's correlation coefficient will be calculated to assess the potential linear association between two continuous variables based on the normality of data. Due to the nature of exploratory study, the regression models will be explored if there is any significant difference identified from the results of previously described statistical testing.

Conducting Analysis

Statistical analysis will be performed using the R language (R Core Team [2018]. R: A language and environment for statistical computing. R Foundation for Statistical Computing, Vienna, Austria. URL <https://www.R-project.org/>) or SAS software, Version 9.4 for Windows (SAS Institute Inc., Cary NC, USA. URL <http://www.SAS.com>).

Power and Sample Size

There is no existing study from which the reductions in NRS score were compared among the three doses of interest. Therefore, this study is considered an exploratory study to explore the possible reduction in NRS score as well as the chance of developing adverse events under a randomized clinical trial setting. With the consideration of both efficacy and safety, we propose including 60 subjects in each group in order to get more information regarding the safety for planning on a larger scale study.

After finishing the exploratory study, based on the mean reduction in each group, if we can find the potential clinical benefits are important, we will then estimate the necessary sample size in order to show the statistical significance. For example, if we can find the potential of clinical importance in primary outcome (such as a mean difference of 1.25 between consecutive doses with the standard deviation of 3.4), in order to show that the reductions are different among doses, with the significant level of 0.05 and power of 80%, if we want to have equal number of

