Side Effects Rating Scale: 0 = No Change / 1 = Weak / 2 = Modest / 3 = Bothersome / 4 = Very Bothersome

	15 Minutes	30 Minutes	60 Minutes	90 Minutes	120 Minutes
Pain Score (0-10):					
	Side Effect Rating Scale Score (0 - 4)				
Fatigue					
Dizziness					
Nausea					
Headache					
Feeling of unreality					
Changes in hearing					
Changes in vision					
Mood changes					
Generalized discomfort					
Hallucination					
Rescue Analgesia Needed? (Y/N)					
Vital signs at 120 minutes or discharge	SBP:		HR:		RR:

Name of Provider Collecting Data

Signature of Provider Collecting Data

/

XIX. Appendix B

Hackensack Meridian Health
Hackensack University Medical Center Campus
 IV Medication Guidelines

**IV SUBANESTHETIC KETAMINE FOR ACUTE PAIN MANAGEMENT
 IN THE ADULT EMERGENCY and TRAUMA CENTER (ETC)**

SCOPE

- Patients under the care of the ETC may receive IV ketamine for the management of acute pain under the direct supervision of an attending physician
- Registered nurses in the ETC may administer IV ketamine for treatment of acute pain as an intermittent infusion in doses not to exceed those outlined in this guideline
- The use of IV ketamine for procedural sedation is outside of the scope of this guideline and is described elsewhere

INDICATIONS

- Ketamine can be used as single agent or as a part of a multi-modal pain regimen for the treatment of moderate or severe pain. Interest in ketamine has emerged as an alternative to opioid analgesics to reduce the overall exposure to opioids and potential for abuse.
- Sub-anesthetic doses of ketamine have demonstrated efficacy in the treatment of various pain types: abdominal, flank, back, musculoskeletal, complex regional pain syndrome, neuropathic and radicular pain, and sickle cell crisis

THERAPEUTIC CATEGORY

Anesthetic agent with analgesic properties

CLINICAL PHARMACOLOGY

Rapid acting anesthetic with analgesic properties associated with the endogenous release of catecholamines, which may elevate blood pressure and heart rate with minimal respiratory depression at analgesic doses.

MECHANISM OF ACTION

- Central and peripheral non-competitive antagonist of N-methyl-D-aspartate (NMDA) receptors
- Inhibits serotonin and dopamine reuptake and inhibits voltage-gated sodium and potassium channels

PHARMACOKINETICS

- Onset of action: 30 seconds
- Duration: Variable for analgesic effect (2-4 hours)
- Metabolism: Hepatic; metabolite: norketamine (25% activity of parent compound)
- Half-life: 2.5 hours

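### Side-effect severity is an ordered 0-4 outcome, but section IX assigns it no test, and its most natural reading leads to tests that ignore the order

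*Combined protocol and SAP*

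**What the plan says.** Section VIII (Methodology) lists "incidence and severity of adverse drug events" among the outcomes and adds: "Incidence, severity, and total number of adverse drug events will be documented", with SERSDA as the instrument. The form in Appendix A gives the grades: "Side Effects Rating Scale: 0 = No Change / 1 = Weak / 2 = Modest / 3 = Bothersome / 4 = Very Bothersome". Ten items are graded at 15, 30, 60, 90 and 120 minutes.

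Section I words the safety objective as a count: "This study will also examine the frequency of adverse events secondary to ketamine".

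Section IX recognises two kinds of variable.
- Continuous variables get the t-test or Wilcoxon test for two groups. For three groups they get ANOVA with Tukey, or Kruskal-Wallis with Dunn if normality or equal variance fails.
- For the rest, Describing Data says: "The discrete variables (such as sex) will be summarized using frequency and percentage". Exploring Differences says: "The chi-square test will be used to compare the categorical variables between or among groups", with Fisher's exact test if any expected count is below 5.

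There is no ordinal class. Section IX does not mention severity or SERSDA, and it does not say how five time points become one value per patient.

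**The concern.** A five-level labelled grade is discrete, so the most natural literal reading sends it to a 3 x 5 chi-square or Fisher test. That test treats weak and very bothersome as unrelated labels. The other route suggested by the text is the frequency of section I, which counts a grade 1 the same as a grade 4. Neither uses the order of the grades.

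Both tests are valid, so the false-positive rate is not the issue. The stake is sensitivity. Section IX justifies 60 patients per group by the wish to learn about safety, and a shift towards worse grades at higher doses is one of the patterns such a trial should be able to detect. There is a second stake: two defensible readings of section IX give different tests, and nothing fixes the choice before the data are seen.

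**Working it through.** **The plan's own figure.** There is none for side effects. The only sample-size figure, 157 per group in section IX, concerns pain scores (difference 1.25, SD 3.4, 80% power). It reproduces exactly with a two-sided t-test at alpha 0.05/3. It has no bearing on severity.

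**Inputs from the protocol.** Three arms of 60 (N = 180), two-sided alpha 0.05, grades 0-4, and the expected-count rule for Fisher.

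**Assumptions, because the documents give no SERSDA rates.** One item with one grade per patient. The share rated 0 in the lowest-dose arm ranges from 85% to 20%. The shift is proportional-odds with odds ratio (OR) 1.3 to 2.5 per dose step:

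logit P(grade ≥ g, dose j) = logit P(grade ≥ g, lowest dose) + (j − 1) ln OR, for j = 1, 2, 3.

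To show what this means, take 50% with any effect and 15% at grade 3 or above at the lowest dose, with OR 1.5.
- Any effect: odds 1, 1.5, 2.25, so 50%, 1.5/2.5 = 60%, 2.25/3.25 = 69%.
- Grade 3 or above: odds 0.15/0.85 = 0.176, 0.265, 0.397, so 15%, 0.265/1.265 = 21%, 0.397/1.397 = 28%.

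**Tests compared.**
- 3 x 5 chi-square: sum of (O − E)²/E on (3 − 1)(5 − 1) = 8 df.
- Any versus none: the same statistic on (3 − 1)(2 − 1) = 2 df.
- Kruskal-Wallis, 2 df: H = [12/(N(N + 1)) Σ R_j²/60 − 3(N + 1)] / [1 − Σ(t³ − t)/(N³ − N)], where R_j are the arms' rank sums and t the numbers tied at each grade.

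**Result 1: the plan's rule (Fisher if an expected count is below 5, otherwise chi-square) against Kruskal-Wallis.** Power in %, 1,000 simulated trials per cell:

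| Rated 0 at lowest dose | OR 1.3 | OR 1.5 | OR 1.75 | OR 2 |
|---|---|---|---|---|
| 85% | 11.5 v 17.8 | 22.1 v 33.8 | 44.1 v 64.1 | 67.2 v 87.1 |
| 70% | 14.8 v 23.0 | 30.2 v 49.6 | 57.4 v 80.9 | 80.6 v 94.8 |
| 50% | 15.8 v 26.2 | 35.1 v 56.5 | 63.5 v 85.9 | 85.6 v 96.7 |
| 30% | 14.7 v 27.6 | 35.7 v 58.5 | 64.4 v 86.3 | 88.5 v 96.6 |

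The smallest gap is 17.8 − 11.5 = 6.3 points and the largest is 80.9 − 57.4 = 23.5. Each power has a simulation standard error of at most √(0.25/1000) = 1.6 points.

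**Result 2: plain 3 x 5 chi-square against Kruskal-Wallis** (6,000 trials per cell, wider range). The gain is 8-14 points at OR 1.3, 18-25 at 1.5, 21-28 at 1.75, 10-24 at 2 and 1-7 at 2.5. It shrinks at the top because every test is then close to full power.

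**Result 3: any versus none against Kruskal-Wallis.** The gain is about 0-4 points when 70-85% are rated 0, 2-13 when 50% are, and up to about 44 when only 20% are.

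**Cross-check.** A separate simulation at OR 1.6 (4,000 trials; 70%, 50%, 30% rated 0) gave 38/47/49% for the 3 x 5 chi-square, 60/60/46% for any versus none and 64/72/73% for Kruskal-Wallis. The type I error of Kruskal-Wallis was 4.7-5.0%. At this OR the 3 x 5 and Kruskal-Wallis tests disagreed on significance in about 30% of trials.

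**The case against.** The strongest reply is that the plan never sends severity to chi-square. Its only example of a discrete variable is sex. The 0-10 pain rating, also whole numbers, is analysed by mean reduction, and Appendix A calls the side-effect rating a score. Handled the same way, severity would go to ANOVA. In simulation Shapiro-Wilk rejected normality in every trial, so that route would end in Kruskal-Wallis with nothing lost. This stands: the firm finding is that the test is unspecified. It does not dispose of the point, because the labelled grades fit the discrete class at least as well and the two readings often disagree.

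The reply also has force on three other counts.
- Section I asks about frequency, for which chi-square/Fisher is suitable, and the trial is exploratory with no power target for safety. But section VIII lists severity as an outcome in its own right.
- The background's report of greater severity comes from ketamine against morphine. The one dose comparison it describes, ketamine added to morphine, reports dizziness more often at the higher dose. So the documents do not show that a severity gradient is expected.
- Every scenario above is a proportional-odds shift, which suits a rank test. The loss if the effect is not monotone was not quantified.

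A reader might infer that the plan prescribes chi-square for severity and so forfeits a fixed 17 to 27 points of power. The documents support neither part. No passage makes that assignment, and figures of that size hold only for mid-range effects, at roughly OR 1.4-1.75 per step, against the full 3 x 5 test.

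**Conclusion.** The point holds as a gap in specification with a material but assumption-dependent cost. Severity is a listed, ordered outcome with no named test. The most natural literal route and the any-versus-none route both ignore the order, and only a continuous reading reaches a test that uses it.

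Under proportional odds with 60 per group, Kruskal-Wallis gains about 6 to 24 points over the plan's chi-square/Fisher rule (OR 1.3-2 per step, 30-85% rated 0). Over the plain 3 x 5 chi-square it gains about 1 to 28 points (OR 1.3-2.5). Over any versus none the gain is negligible when the side effect is uncommon and large only when most patients have it.

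These figures are for a single item with one grade per patient and assumed rates. The concern is the order of the grades, not of the doses, since Kruskal-Wallis does not use dose order either. The gap should be closed, but it does not invalidate the trial or the incidence comparison.

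**What to change.** Add to section IX:
- SERSDA item severity (0-4) is an ordinal outcome.
- Each patient contributes one summary per item, for example the worst grade over the 120-minute follow-up. Since section VIII ends assessment at discharge, state how earlier discharge is handled.
- The summary is compared among the three doses with the tie-corrected Kruskal-Wallis test, then Dunn, both already in the plan. A proportional-odds model reporting a common odds ratio with 95% CI is an alternative.
- Chi-square/Fisher is kept for incidence and other binary or nominal variables. Any-grade and grade 3 or above frequencies are shown by dose beside the severity result.

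The cost is a few sentences, with no new data, patients or visits. The downside is small: a rank result is less direct to read than a percentage and less sensitive to a non-monotone effect. The frequencies shown alongside help with both.

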25. Food and Drug Administration (FDA). Extended-release (ER) and long-acting (LA) opioid analgesics Risk Evaluation and Mitigation Strategy (REMS). www.fda.gov/downloads/drugs/drugsafety/postmarketdrugsafetyinformationforpatientsandproviders/ucm311290.pdf. Accessed September 20th, 2018.

XVIII. Appendix A

Demographics				
Subject #:	Date/Time:		Age:	Sex: Male / Female
Opioid Tolerant?*:  Yes  No	Weight (kg):	SBP:	HR:	RR:
Initial Pain Score Immediately Prior to Randomization (0-10):				

*Opioid tolerant: Patients receiving, for one week or longer, at least 60 mg oral morphine/day, 25 mcg transdermal fentanyl/hour, 30 mg oral oxycodone/day, 8 mg oral hydromorphone/day, 25 mg oral oxymorphone/day, or an equianalgesic dose of another opioid
				
Eligibility				

If the subject does not meet all of the eligibility criteria, do not proceed with randomization.
				

Inclusion Criteria (if any answer is “no”, stop immediately):
				

1) Acute pain (including acute or chronic)?
 
Type of Pain (Circle)
 
Abdominal
 
Flank
 
Back
 
Musculoskeletal
 
Complex Regional Pain Syndrome
 
Neuropathic
 
Radicular
 
Sickle Cell
 
Trauma
 
Other _____
				

2) NRS pain score $\geq 4/10$?
 
3) Provider determines the patient requires intravenous ketamine?
				

Exclusion Criteria (if any answer is “yes”, stop immediately):
				

1) History of hypersensitivity to ketamine?
 
2) Altered mental status?
 
3) Pregnant or breastfeeding?
 
4) Psychiatric Illness?
 
5) Known history of renal or hepatic insufficiency?
 
6) Acute head or eye injury?
 
7) Suspected intracranial hypertension or mass?
 
8) Headache as the chief complaint?
 
9) Alcohol or drug abuse?
 
10) Received an analgesic within the last 4 hours?
 
11) History of congestive heart failure?
 
12) History of aortic or brain aneurysm?
 
13) Active chest pain?
 
14) History of porphyria?
 
15) Active methadone treatment?
				

16) Signs of respiratory, hemodynamic, or neurologic compromise?

Defined as SBP < 90 mmHg or > 180 mmHg, HR < 50 or > 150, RR < 10 or > 30, or GCS < 15.

17) Previously received ketamine \leq 0.3 mg/kg IV for acute pain in the emergency department

I have reviewed all of the inclusion and exclusion criteria and the patient is a candidate for this study: Yes No

Treatment

Side Effects Rating Scale: 0 = No Change / 1 = Weak / 2 = Modest / 3 = Bothersome / 4 = Very Bothersome

	15 Minutes	30 Minutes	60 Minutes	90 Minutes	120 Minutes
Pain Score (0-10):					
	Side Effect Rating Scale Score (0 - 4)				
Fatigue					
Dizziness					
Nausea					
Headache					
Feeling of unreality					
Changes in hearing					
Changes in vision					
Mood changes					
Generalized discomfort					
Hallucination					
Rescue Analgesia Needed? (Y/N)					
Vital signs at 120 minutes or discharge	SBP:		HR:		RR:

Name of Provider Collecting Data

Signature of Provider Collecting Data

/

XIX. Appendix B

Hackensack Meridian Health
Hackensack University Medical Center Campus
 IV Medication Guidelines

**IV SUBANESTHETIC KETAMINE FOR ACUTE PAIN MANAGEMENT
 IN THE ADULT EMERGENCY and TRAUMA CENTER (ETC)**

SCOPE

- Patients under the care of the ETC may receive IV ketamine for the management of acute pain under the direct supervision of an attending physician
- Registered nurses in the ETC may administer IV ketamine for treatment of acute pain as an intermittent infusion in doses not to exceed those outlined in this guideline
- The use of IV ketamine for procedural sedation is outside of the scope of this guideline and is described elsewhere

INDICATIONS

- Ketamine can be used as single agent or as a part of a multi-modal pain regimen for the treatment of moderate or severe pain. Interest in ketamine has emerged as an alternative to opioid analgesics to reduce the overall exposure to opioids and potential for abuse.
- Sub-anesthetic doses of ketamine have demonstrated efficacy in the treatment of various pain types: abdominal, flank, back, musculoskeletal, complex regional pain syndrome, neuropathic and radicular pain, and sickle cell crisis

THERAPEUTIC CATEGORY

Anesthetic agent with analgesic properties

CLINICAL PHARMACOLOGY

Rapid acting anesthetic with analgesic properties associated with the endogenous release of catecholamines, which may elevate blood pressure and heart rate with minimal respiratory depression at analgesic doses.

MECHANISM OF ACTION

- Central and peripheral non-competitive antagonist of N-methyl-D-aspartate (NMDA) receptors
- Inhibits serotonin and dopamine reuptake and inhibits voltage-gated sodium and potassium channels

PHARMACOKINETICS

- Onset of action: 30 seconds
- Duration: Variable for analgesic effect (2-4 hours)
- Metabolism: Hepatic; metabolite: norketamine (25% activity of parent compound)
- Half-life: 2.5 hours

CONTRAINDICATIONS

 • Hypersensitivity to ketamine • SBP > 180 and DBP > 100 mmHg • HR < 50 or > 150 bpm • Elevated intracranial pressure • Increased intraocular pressure • Pregnant or breastfeeding • Acute head or eye injury 	
 • Congestive heart failure - stage III and IV (myocardial depressant effects) • Aneurysm • Angina • Psychiatric disorders • Porphyria • Active methadone treatment
---	---

RELATIVE CONTRAINDICATIONS

- SBP <90 or > 140 mmHg
- Renal or hepatic insufficiency
- Alcohol or drug abuse
- Coronary artery disease

PRECAUTIONS

- Emergence reactions (vivid dreams, hallucinations, frank delirium, confusion, excitement, or irrational behavior) are dose-related but may occur at the subanesthetic doses used for treatment of acute pain
- Patients > 65 years old

DOSAGE AND ADMINISTRATION

1. Dosages:

- Single dose of 0.1 – 0.3 mg/kg/dose (maximum single dose: 30mg) administered over 20 minutes via intermittent infusion
 - Lower doses should be initiated for elderly patients or those with renal/hepatic dysfunction
 - Doses greater than 0.3 mg/kg/dose may lead to dissociative effects
- Dose may be repeated after 60 minutes up to a total cumulative dose of 0.3mg/kg or 30mg
- An additional dose may be repeated after 4 hours for patients requiring ongoing analgesia while remaining in the ED

2. Standard Dilution: Weight based dose diluted into 100 mL D5W or NS

TREATMENT OF EMERGENCE REACTION

- Emergence reaction may be treated with short acting benzodiazepines
- Midazolam 1mg IV once (0.5mg IV in the elderly) administered by the provider is typically sufficient
 - Doses may be repeated if necessary

DRUG INTERACTIONS

Ketamine is a substrate for CYP2B6, CYP2C9, & CYP3A4. The following includes, but is not limited to a list of drugs that may increase the levels/effects of ketamine.

- Sertraline, paroxetine (2B6)
- Fluconazole, nicardipine, NSAIDs, sulfonamides (2C9)
- Azole antifungals, clarithromycin, propofol, nicardipine (3A4)

ADVERSE REACTIONS

● Hypertension● Tachycardia/bradycardia● Tonic/clonic movements, tremor● Increased intracranial pressure● Emergence reaction/ dissociative effects (vivid dreams, hallucinations, frank delirium, confusion, excitement, or irrational behavior)	
● Visual disturbances (diplopia and nystagmus)● Nausea, vomiting● Skin rash● Headache● Fatigue
--	--

